## **Study Population**

Individuals will be eligible if they meet the following criteria: age  $\geq 18$ -39 years at the time of consent, diagnosed with invasive cancer malignancy between the ages of 15-39 years, diagnosed with invasive malignancy in the last 10 years, with no evidence of progressive disease or second primary cancers, completed active cancer directed therapy (cytotoxic chemotherapy, radiation therapy and/or definitive surgical intervention), except may be receiving “maintenance” therapy to prevent recurrences, have no pre-existing medical condition(s) that preclude adherence to an unsupervised exercise program including cardiovascular disease, congestive heart failure, pulmonary conditions, renal disease, and severe orthopedic conditions, not currently meeting guideline recommendations of 150 MVPA minutes/week (self-report) and guideline recommendations for fruit and vegetable consumption, have the ability to read, write and speak English, have access to the Internet on at least a weekly basis, possess and usage of an Internet e-mail address or willingness to sign up for a free email account (e.g., Gmail), have smartphone with internet access and text messaging plan and be willing to be randomized to any condition.

Exclusion criteria include a history of heart attack or stroke within past 6 months; untreated hypertension, hyperlipidemia, or diabetes, unless permission is provided by their health care provider; health problems which preclude ability to walk for PA; a heart condition, chest pain, or other health problems that influence the ability to follow physical activity recommendations; plans for major surgery (e.g., breast reconstruction) during the study time frame; currently using prescription weight loss medications; currently pregnant, pregnant within the past 6 months, or planning to become pregnant within the next 6 months; report a past diagnosis of or receiving treatment for an eating disorder; hospitalization for depression or another psychiatric disorder in the past 12 months or history of bipolar or other psychotic disorder; currently participating in another weight loss, nutrition, or physical activity study or program; already adherent to the American Cancer Society’s recommendation of exercising  $> 150$  minutes/week of moderate-to-vigorous intensity PA and the American Cancer Society’s recommendation of consuming  $> 5$  servings of fruits and vegetables/day.

Individuals that reported joint problems, some prescription medications, or current treatment for hypertension or hyperlipidemia will be required to obtain written physician consent to participate (Appendix).

The trial is registered on clinicaltrials.gov (NCT05887401) and was approved by the Institutional Review Board at the University of North Carolina at Chapel Hill on August 18, 2022.

## **3. STUDY PROCEDURES**

### **Data Collection**

All study participants will complete objective weight measurements, two dietary recalls, and self-administered online surveys at baseline and 3 months (post-intervention). At 6 weeks, only psychosocial measures and medical events will be collected via online survey and telephone. Participants will receive \$25 for completing the 3-month assessments. Online surveys will include measures of theoretical mediators, other psychosocial constructs, and process measures. We will send emails and texts prompting participants to complete assessments, with follow-up emails and phone calls to non-respondents, as necessary. Measures and timing are described below.

## Measures

### ***Behavioral Measures (collected at baseline and 3 months)***

Device-measured physical activity will be assessed at baseline and 3 months using the study provided activity tracker. Participants will be instructed to wear the device at all times for a full week; monitoring for at least 600 min/day for at least 4 days in the week (including at least one weekday and one weekend day) is considered adequate for analysis. Data are transmitted to Fitbit each time the participant syncs their tracker with the Fitbit app on their phone. Weekly minutes of moderate-to-vigorous activity (termed “active minutes” in Fitbit) and steps per day will be computed from the participant’s Fitbit data and averaged over a minimum of 4 out of a 7-day period.

Self-reported physical activity will be assessed using the Paffenbarger Activity Scale (PAQ), which assesses leisure-time activity. The PAQ provides an estimate of minutes per week of moderate-to-vigorous intensity, and calories/week of light (5 kcal/min), medium (7.5 kcal/min), and high (10 kcal/min) intensity activities. PAQ changes have been predictive of weight change.

Dietary Intake: Changes in dietary intake will be assessed using the NCI’s 24-hour Recall (ASA-24) by trained administrators. Participants will complete two self-reported recalls; one weekday and one weekend day. The 24 recall is a validated method of measuring diet. Using two recalls permits adjustment of estimates for intraindividual variation and is superior to administering one recall. We will examine change in overall energy intake and saturated fat intake, as well as change in fruit and vegetable consumption, fiber consumption, and change in the Healthy Eating Index score.

Healthy Eating Index: The HEI-2020^78 consists of 13 component scores, including: total fruit, whole fruit, total protein foods, total vegetables, greens and beans, whole grains, dairy, seafood and plant proteins, fatty acids, sodium, refined grains, added sugars, and saturated fats. The summation of the 13 component scores ranges from 0 to 100, with higher scores indicating closer compliance with the 2020 DGA.

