**Exclusion Criteria**

1. History of heart attack or stroke within past 6 months
2. Untreated hypertension, hyperlipidemia, or diabetes, unless permission is provided by their health care provider.
3. Health problems which preclude ability to walk for PA
4. Report a heart condition, chest pain during periods of activity or rest, or loss of consciousness on the Physical Activity Readiness Questionnaire (PAR-Q; items 1-4).
5. Report a past diagnosis of or receiving treatment for a DSM-IV-TR eating disorder (anorexia nervosa or bulimia nervosa).
6. Currently pregnant, pregnant within the past 6 months, or planning to become pregnant within the next 6 months.
7. Hospitalization for depression or other psychiatric disorder within the past 12 months. History of psychotic disorder or bipolar disorder.
8. Plans for major surgery (e.g., breast reconstruction) during the study time

---

frame

9. Currently participating in a weight loss, nutrition or physical activity study or program or other study that would interfere with this study.
10. Currently using prescription weight loss medications

Number Of Subjects	72
Study Duration	Each subject's participation will last 4 months.
Study Phases	
Screening	(1) Screening : screening for eligibility and obtaining consent and (2) Baseline assessment
Study Treatment	(3) Intervention : study intervention/experimental treatment.
Follow-Up	(4) Follow-up assessment will occur at 6 weeks and 3 months
Efficacy Evaluations	NA
Pharmacokinetic Evaluations	NA
Safety Evaluations	All medical events and safety data will be assessed at assessment points or when interim events are reported by participants using a standard form used in our ongoing NIH funded trials.
Statistical And Analytic Plan	
The primary objective is to evaluate the feasibility and acceptability of a digital intervention components to increase PA and improve nutrition behaviors among YACS (n=80) at 3 months. Our primary feasibility measures are participation, accrual, and retention rates.
 
The secondary outcome analysis will use mixed effects models to test for differences in MVPA and HEI by intervention components across time (baseline, 6 weeks, and 3 months). Effects will be modeled as component x time interactions with the 3-month outcome as the primary endpoint.

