Using a factorial experiment, we will test main effects of each of 4 candidate intervention components and interactions between the components, making efficient use of a smaller sample size than a typical RCT would require. We propose to conduct a 3-month, 2 full factorial trial testing the effects of four intervention components—each with two levels—including (Table 1):

- 1) simplified dietary tracking based on TLA (daily tracking of green (low-calorie, high nutrients) vs. red (high-calorie, high-fat, low nutrients) foods),
- 2) dietary goals using TLA (daily goals vs. no goals),
- 3) supportive text messages (yes vs. no),
- 4) lesson delivery (all provided once vs. weekly).

Proposed intervention strategies and components are based on previous nutrition and PA interventions that have been conducted in cancer survivors targeting these health behaviors. The conceptual model guiding intervention development includes theoretical constructs from social cognitive theory (SCT) and self-determination theory (SDT); intervention strategies will incorporate behavior change techniques (BCTs) that have demonstrated efficacy in previous behavioral interventions in cancer survivors. Intervention components will target the SDT and SCT constructs associated with improved dietary and PA behaviors: perceived autonomy (self-efficacy and self-regulation through goal setting and self-monitoring of behaviors), perceived competence (behavioral capability, perceived barriers, and outcome expectations targeted with behavioral lessons and feedback), and perceived relatedness (social support from text message and tailored feedback on goals and progress).

The primary outcomes of interest are feasibility and acceptability. Secondary outcomes include change in minutes/week of MVPA and HEI dietary quality index score.

Assessments of outcomes will be conducted at baseline, 6 weeks, and 3 months (post-intervention). We hypothesize that it will be feasible to recruit and retain post-treatment YACS for this intervention. We also hypothesize that the intervention will be acceptable to YACS participants. We will examine recruitment potential, retention, pilot intervention procedures, satisfaction, and adherence to the intervention.

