#### *Elements Common to All Experimental Conditions*

Core Intervention (n=80) all participants will receive a core intervention that includes PA and nutrition education modified from concepts of the Diabetes Prevention Program , our prior studies , and based around the consensus guideline recommendations for cancer survivors. Participants will be given digital tools to facilitate self-monitoring – a PA tracker and simplified diet tracking tool to support self-regulation of behaviors. The intervention will be delivered a mobile app integrated with Fitbit. Participants will receive an activity tracker (Fitbit) in the mail, followed by an introductory videochat session with an interventionist. In this session they will receive information relevant to their participation in the program, including an overview of how to use the study app (for both iOS and Android); Fitbit; the Traffic Light Log; how to self-monitor to achieve their daily goals (eating, activity, and self-weighing), and other information relevant to the conditions to which they have been randomized. Activity and dietary data are synced to study servers and activity is available in the app on pages that display participants' daily and overall progress towards their goals. The study app also includes 12 behavioral lessons that are delivered based on randomization. These include behavioral strategies with specific instruction on core cognitive and behavioral skills (i.e., goal setting, self-monitoring, problem solving, overcoming barriers, reaching out for social support, and cognitive restructuring).

Participants will receive qualitative feedback on self-monitoring behaviors and goal progress specific to MVPA and diet tracking (and goals). Feedback will include positive reinforcement and encouragement, strategies for barrier identification and overcoming barriers, and strategies for improving dietary and PA behaviors. Participants will receive tailored feedback summaries weekly. Participants will receive an email directing them to their feedback page. The feedback message will include feedback based on participants' number of days tracking diet and PA, and progress toward goals.

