***Process and Adherence Measures (collected over 6 months)***

*Dietary Monitoring.* Engagement will be assessed via frequency of dietary monitoring. Each food entry will be time-stamped and automatically captured by the study website interface. Frequency of dietary monitoring will be defined as the total number of days during the 3-month intervention that participants tracked breakfast or lunch AND dinner, which will be considered a full (versus partial) day of tracking.

*PA monitoring.* Objective self-monitoring of PA will be assessed via the Fitbit tracker data for all groups. Data will be collected using the Fitbit application program interface (API). We will collect data on frequency and number of days that activity was tracked using the Fitbit (steps>500/day). These data will be tabulated to derive a measure of percent of days in which activity was tracked, and average activity tracking days per week. We will also ask participants how often they viewed the Fitbit website/mobile app to access graphs of their physical activity trends.

*Adherence to Dietary Goals.* Adherence will be measured as the total number of full days of tracking (i.e., breakfast or lunch AND dinner) during which participants met their dietary goal. Non-adherence will be assumed for partial days of tracking, or days where participants did not track.

*Engagement measures:* Using REDcap and study specific TLA website analytics we will examine website logins, goal setting, viewing feedback, lesson views, calculated as average logins and component views per week.

*Program Acceptability and Satisfaction.* Participants will be asked to complete a post-treatment program evaluation. Measures will be adapted from previous studies and assess intervention exposure and attention, perceived personal relevance, and satisfaction with intervention components.

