Using maximum likelihood methods, we will use mixed model analyses with repeated measures to estimate changes in MVPA and HEI (and other secondary measures; Objectives 2.1.5-2.1.7) at 3 months and to test for statistical differences across conditions in changes over time, adjusting for age, cancer type, and time since diagnosis. Models will include random intercept, time, component, and component\*time variables. A proper error covariance structure will be chosen based on model fit indicated by model likelihood, Akaike Information Criterion and Bayesian information Criterion.

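### The MVPA model has no defined 6-week value, and the Fitbit weeks between baseline and 3 months go unused for anyone without a valid 3-month week

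*Combined protocol and SAP*

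**What the plan says.** The protocol gives two schedules for MVPA.

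- Section 3, Behavioral Measures: "Device-measured physical activity will be assessed at baseline and 3 months using the study provided activity tracker". For each assessment, "Participants will be instructed to wear the device at all times for a full week". A week counts if there are at least 600 minutes a day on at least 4 days, with at least one weekday and one weekend day.
- Section 3, Data Collection: "At 6 weeks, only psychosocial measures and medical events will be collected via online survey and telephone".
- Synopsis, Statistical and Analytic Plan: mixed models test for "differences in MVPA and HEI by intervention components across time (baseline, 6 weeks, and 3 months"), with 3 months as the main endpoint.
- Section 1, Study Objectives: "Assessments of outcomes will be conducted at baseline, 6 weeks, and 3 months (post-intervention").

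The tracker also supplies data between assessments. Under the core intervention, "Activity and dietary data are synced to study servers", and participants get weekly feedback that draws on days tracked and progress toward goals. The activity goal moves each week with individual progress. Under PA monitoring, "Data will be collected using the Fitbit application program interface (API"), for a count of days tracked.

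For the analysis, "Models will include random intercept, time, component" and component-by-time terms, fitted by maximum likelihood with adjustment for age, cancer type and time since diagnosis. The error structure is to be chosen on fit. Handling Missing Data plans multiple imputation if data are judged missing completely at random or at random. Its 5% trigger refers to predictor variables. Neither section names the interim Fitbit weeks as an outcome or an imputation input.

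**The concern.** There are two linked problems.

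First, the three-time-point model cannot be fitted to MVPA as the measures are written. No 6-week tracker week, window or wear rule is defined.

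Second, if the measures section governs, each person has at most one post-baseline MVPA value. Someone with no valid 3-month week enters the model with baseline and covariates only. The estimate for that person then follows others at the same component levels with similar baseline and covariates, whatever their tracker showed in the weeks before they were lost.

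In a digital programme, people whose activity is falling may be the ones who leave. The plan itself raises a way in which this could differ by component: it says that text messages may add burden and lower efficacy. If loss tracks activity at one level of a factor and not at the other, the comparison favours the level that loses its less active people. Missing at random given baseline alone then fails. Given the weekly values it becomes more credible.

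**Working it through.** **1. Is there a 6-week MVPA value?** The synopsis and objectives say yes. Data Collection limits 6 weeks to psychosocial measures and medical events, and the behavioral measures are headed baseline and 3 months. Both cannot stand.

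**2. How many people are affected?** The documents give no MVPA standard deviation, effect size or power, so there is no stated figure to reproduce. The only drop-out figures are the retention hypotheses (70% null, 90% alternative) and the two cut-offs (66 and 62 of 80). Retention stands in here for having a valid 3-month week.

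| Retained of 80 | No 3-month value | Detectable main effect (SD) |
|---|---|---|
| 80 | 0 | 0.63 |
| 72 (90%) | 8 | 0.66 |
| 66 | 14 | 0.69 |
| 62 | 18 | 0.71 |
| 56 (70%) | 24 | 0.75 |

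The last column is (1.96 + 0.84) × √(2/n per level), with n per level half the number retained; two-sided 5% and 80% power are assumptions. The synopsis lists 72 subjects; on that base the range is 72 × 0.10 = 7.2 to 72 × 0.30 = 21.6.

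**3. How large could the bias be?** Simulation with no true effect, 40 per level and 13 weekly values. Assumed SDs are 60 between persons, 50 for an AR(1) part (correlation 0.8) and 25 residual, so weekly SD = √(3600 + 2500 + 625) = 82 min. The weekly chance of stopping depends on the current week's MVPA at one level and is constant at the other. The model is generalised least squares with known covariance. Ranges cover three sets of drop-out settings for the first and last columns and two for the middle one; simulation error is about 0.7 to 0.8 where it was recorded.

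| Missing at week 12 | Bias, weeks 0 and 12 | Bias, weeks 0, 6, 12 | Bias, weeks 0 to 12 |
|---|---|---|---|
| about 12% | 2.5 to 2.8 min/week | 1.6 to 1.8 | within 0.6 of zero |
| about 28% | 5.6 to 7.2 min/week | 3.5 to 3.6 | within 0.9 of zero |

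Against the standard error, in the setting with the largest bias at 28%: 2.67/15.99 = 0.17 and 7.15/17.81 = 0.40. Against the weekly SD: 2.67/82 = 0.03 and 7.15/82 = 0.09. A single 6-week value removes a little over a third of the bias (for example 1 − 3.6/5.6 = 0.36).

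**4. What is gained in precision?** In the same setting the standard error goes from 15.99 to 15.78 (1.3% lower) and from 17.81 to 17.25 (3.1% lower). A formula check: effective n = n_obs / (1 − (m/N) × partial R²), with partial R² = (R² − 0.5²)/(1 − 0.5²). It assumes a baseline correlation of 0.5, a multiple correlation R of 0.6 to 0.8 once interim weeks are added, and a usable interim week for every person lost. Effective n rises from 72 to 73–76 at 90% retention and from 56 to 59–66 at 70%. Even the best case, √(56/66.4) = 0.92, is a standard error about 8% lower.

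**5. Where does the remedy fall short?**
- If stopping depends on the coming, unobserved week, all 13 weeks still leave about 0.8 min/week of bias at 12% missing and 2.5 to 2.9 at 28%.
- With a random intercept as the only covariance over 13 weeks, one set of runs gave a model standard error of 15.0 against an empirical 18.2: 1 − 15.0/18.2 = 18% too small. Another gave 22 to 28%. A nominal 5% test then rejects at 2 × [1 − Φ(1.96 × 15.0/18.2)] = 11%, and at 28% too small at 2 × [1 − Φ(1.96 × 0.72)] = 16%.

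**The case against.** A pre- and post-assessment week is a legitimate choice for a secondary outcome in a feasibility pilot, and the protocol concedes that its effect sizes may not be conclusive. The bias is a fraction of a standard error. It rests on assumed variances and on drop-out that depends on activity at one level only, and the larger figure needs about as much loss as the plan's null retention value. The near-zero result with all weeks follows from letting stopping depend on observed values. Moving to 13 time points in 80 people adds a covariance problem that two points largely avoid. All of this stands, and it limits how much weight the point can carry.

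Four stronger readings are tempting but not supported:

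- *MVPA is measured at two times and no others.* The measures section says so, but the synopsis and objectives list 6 weeks. On that text a person lost in week 8 would contribute a 6-week value. The certain defect is the contradiction.
- *Everyone who stops the programme is lost.* A person who stops but wears and syncs the tracker in the 3-month week contributes. The gap concerns those without a valid 3-month week.
- *Those people are dropped from the analysis.* Their baseline stays in the likelihood, and multiple imputation is planned. What is missing is any statement that interim weeks inform either.
- *The interim weeks are certainly usable.* The instruction to wear the device at all times concerns the assessment week, and the adherence measure names steps above 500 a day, not wear minutes. People who are disengaging may fail the wear rule.

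**Conclusion.** The point holds in this form. The documents disagree on whether a 6-week MVPA value exists, and the modelled version has no defined input. On the measures text, 8 to 24 of 80 people would have no post-baseline MVPA at 90% to 70% retention, while activity data that bear on their loss reach the study and have no stated role in this outcome.

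The possible bias in a 3-month component effect is about 3 min/week at 12% missing and 6 to 7 at 28%, or 0.2 to 0.4 standard errors. These sizes depend on the assumed SDs, the correlation and a drop-out pattern that differs by component level; the documents supply none of them. The simulated gain in precision is 1 to 4%. The reason to act is that a missing-at-random assumption becomes more credible at little cost. The primary feasibility conclusions are not affected.

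**What to change.** 1. Reconcile the synopsis, Study Objectives, Data Collection and Behavioral Measures on when MVPA is measured. If 6 weeks stays, define its tracker week and apply the same wear rule.
2. Compute MVPA from the Fitbit API for each intervention week that meets the existing wear rule, including weeks before a person is lost.
3. Enter those weeks, at minimum week 6, as repeated measures with categorical time, or use them as auxiliary variables in the imputation model. Keep the component contrast at 3 months as the reported effect.
4. Pre-specify a covariance with serial correlation (for example a random intercept plus AR(1)) or robust standard errors. A random intercept alone should not be used over 13 weeks.
5. Where the 3-month surveys are missed but the tracker week is valid, use that week's MVPA without counting the person as retained.

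The cost is more data processing, an added analysis-plan paragraph and a more complex covariance model. No visit, device or procedure is added. Some interim weeks will fail the wear rule, and bias remains if stopping depends on activity that was not observed.
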